9.1.9 Contraception and Pregnancy Avoidance Procedure

From signing of informed consent, throughout the duration of the study, and for 90 days after last dose of study medication, nonsterilized** male subjects who are sexually active with a female partner of childbearing potential* must use barrier contraception (eg, condom with spermicidal cream or jelly). In addition, they must be advised not to donate sperm during this period.

From signing of informed consent, throughout the duration of the study, and for 90 days after last dose of study medication, female subjects of childbearing potential* who are sexually active with a nonsterilized male partner** must use adequate contraception. In addition they must be advised not to donate ova during this period.

*Females NOT of childbearing potential are defined as those who are pre-menarche with no ovulation ability or have been surgically sterilized (hysterectomy, bilateral oophorectomy or tubal ligation) .

**Sterilized males should be at least 1 year postvasectomy and have confirmed that they have obtained documentation of the absence of sperm in the ejaculate.

An acceptable method of contraception is defined as one that has no higher than a 1% failure rate. In this study, where medications and devices containing hormones are excluded, the only acceptable methods of contraception are:

Barrier methods (each time the subject has intercourse):

- Male condom PLUS spermicide.
- Cap (plus spermicidal cream or jelly) PLUS male condom and spermicide.
- Diaphragm (plus spermicidal cream or jelly) PLUS male condom and spermicide.

Intrauterine devices (IUDs):

- Copper T PLUS condom or spermicide.
- #Progesterone T PLUS condom or spermicide.

Subjects will be provided with information on acceptable methods of contraception as part of the subject informed consent process and will be asked to sign a consent form stating that they understand the requirements for avoidance of pregnancy, donation of ova, and sperm donation during the course of the study.

During the course of the study, regular serum/urine human chorionic gonadotropin (hCG) pregnancy tests will be performed only for female of childbearing potential and subjects will receive continued guidance with respect to the avoidance of pregnancy and sperm donation as part of the study procedures (Appendix A). In addition to a negative serum hCG pregnancy test at Screening, subjects also must have a negative urine hCG pregnancy at test Day –1 or Day 1 prior to receiving any dose of study medication drug administration.

9.1.10 Pregnancy

If any subject is found to be pregnant during the study she should be withdrawn and any sponsor-supplied drug Leuprorelin should be immediately discontinued. In addition, any pregnancies in the partner of a male subject during the study or for 90 days after the last dose, should also be recorded following authorization from the subject's partner.

If the pregnancy occurs during administration of active study medication, eg, after within 30 days of the last dose of active study medication, the pregnancy should be reported immediately, using a pregnancy notification form, to the contact listed in Section 1.0.

If the female subject and/or female partner of a male subject agrees to the primary care physician being informed, the investigator should notify the primary care physician that the subject/female partner of the subject was participating in a clinical study at the time she became pregnant and provide details of treatment the subject received.

All pregnancies in subjects on active study drug including comparator will be followed up to final outcome, using the pregnancy form. Pregnancies will remain blinded to the study team. The outcome, including any premature termination, must be reported to the sponsor. An evaluation after the birth of the child will also be conducted.

9.1.11 ECG Procedure

A standard 12-lead ECG will be recorded. The investigator (or a qualified observer at the investigational site) will interpret the ECG within normal limits, abnormal but not clinically significant, or abnormal and clinically significant.

9.1.12 Bone Age

Bone age will be evaluated by investigators at each site using TW3 standards or Greulich-Pyle standards, and the result will be recorded in the eCRF. All BA x-ray will be sent for central reading before the end of the study. If BA x-ray result is already available – whether in the same hospital or

other hospital - within 28 days prior to first dose, the result be used for screening, under the condition that the Site retain a copy of the data/image in file notes as source documents.

9.1.13 Bone Mineral Density

Bone mineral density will be evaluated by dual energy x-ray bone densitometry at selected sites only. Throughout the study, the same apparatus should be used and operated in the same scan mode for all scans for an individual subject. The results will be recorded in the eCRF.

9.1.14 Cranial MRI

Cranial magnetic resonance imaging MRI will be performed at Screening Visit only. Investigators will assess the presence of any intracranial tumor. The results will be recorded in the eCRF. If Cranial MRI result is already available – whether in the same hospital or other hospital - within 28 days prior to first dose, the result can be used for screening, under the condition that the Site retain a copy of the data/image in file notes as source documents. Cranial MRI can consist of only pituitary scan, including saddle region.

9.1.15 Pelvic/Testicular Ultrasonography

Pelvic ultrasonography will be performed for females to measure ovarian volume, uterus size and volume and number of follicles. For males, ultrasonography will be performed to measure the testicular volume. The results will be recorded in the eCRF.

9.1.16 Documentation of Screen Failure

Investigators must account for all subjects who sign informed consent.

If the subject is found to be not eligible at this visit, the investigator should complete the eCRF.

The primary reason for screen failure is recorded in the eCRF using the following categories:

- PTE/AE.
- Did not meet inclusion criteria or did meet exclusion criteria.
- Significant protocol deviation.
- Lost to follow-up.
- Voluntary withdrawal.
- Study termination.
- Other.

Subject numbers assigned to subjects who fail screening should not be reused.

9.1.17 Documentation of Study Entrance

Only subjects who meet all of the inclusion criteria and none of the exclusion criteria are eligible for entrance into the treatment phase.

If the subject is found to be not eligible for treatment phase, the investigator should record the primary reason for failure on the applicable eCRF.

9.2 Monitoring Subject Treatment Compliance

Subjects will be injected the study medication Leuprorelin 3.75 mg or 1.88 mg on site by investigator or investigator's designee. All supplies used to administer study medication to the subject will be recorded on the eCRFs.

If a subject is persistently noncompliant, defined as missing two consecutively scheduled drug injections against what is stipulated in the protocol's schedule of study procedures, with the study medication Leuprorelin 3.75 mg and 1.88 mg, it may be appropriate to withdraw the subject from the study. All subjects should be re instructed about the dosing requirement during study contacts. The authorized study personnel conducting the re-education must document the process in the subject source records.

9.3 Schedule of Observations and Procedures

The schedule for all study-related procedures for all evaluations is shown in Appendix A. Assessments should be completed at the designated visit.

9.3.1 Screening - Visit 1

Subjects will be screened within 28 days prior to first dose (Week 0, Visit 2). Subjects will be screened in accordance with predefined inclusion and exclusion criteria as described in Section 7.0. See Section 9.1.16 for procedures for documenting screening failures.

Procedures to be completed at Screening (Visit 1) include:

- Informed consent.
- Inclusion/exclusion criteria.
- Demographics, medical history, and medication history.
- Physical examination.
- Vital signs.
- Weight, height
- Concomitant medications.
- Concurrent medical conditions.
- Predicted adult height.

CONFIDENTIAL

- Tanner staging evaluation.
- Bone age.
- Hematology, Urine analysis, clinical chemistry laboratory tests.
- Pregnancy avoidance counseling, for female subject who, at the discretion of the investigator, is deemed to be of childbearing potential or , the male subject who is nonsterilized and sexually active with a female partner of childbearing potential.
- ECG.
- Pelvic/testicular ultrasonography.
- Stimulation test.
- Cranial MRI.
- CEA, AFP, β -HCG.
- PTE assessment.
- Assign subject number.

9.3.2 Study Entrance - Visit 2 (Week 0, first dose)

Study entrance will take place on Day 1 (Visit 2). The following procedures will be performed and documented during Study Entrance:

- Vital signs.
- Weight, height
- Concomitant medications.
- Tanner staging evaluation.
- Urine Pregnancy test.
- Pregnancy avoidance counseling, for female subject who, at the discretion of the investigator, is deemed to be of childbearing potential or , the male subject who is nonsterilized and sexually active with a female partner of childbearing potential.
- Estradiol or testosterone.
- Bone mineral density.
- Serum bone metabolism biomarker.
- Injection of investigational drug by investigator or investigator's designee.
- PTE assessment.
- AE assessment.

If the subject has satisfied all of the inclusion criteria and none of the exclusion criteria for study entrance, the subject should be assigned a subject number. Subjects will be instructed on when to take the first dose of investigational drug as described in Section 6.1. The procedure for documenting Screening failures is provided in Section 9.1.16.

9.3.3 Treatment Phase - Visit 3 (Week 12)

Visit 3 will take place on Week 12. The following procedures will be performed and documented during this visit:

- Vital signs.
- Weight, height.
- Concomitant medications.
- Tanner staging evaluation.
- Pregnancy avoidance counseling, for female subject who, at the discretion of the investigator, is deemed to be of childbearing potential or , the male subject who is nonsterilized and sexually active with a female partner of childbearing potential.
- ECG.
- Estradiol or testosterone.
- Stimulation test.
- Injection of Investigational Drug by investigator or investigator's designee.
- AE assessment.

9.3.4 Treatment Phase - Visit 4 (Week 24)

Visit 4 will take place on Week 24. The following procedures will be performed and documented during this visit:

- Vital signs.
- Weight, height.
- Concomitant medications.
- Tanner staging evaluation.
- Bone age.
- Hematology.
- Pregnancy avoidance counseling, for female subject who, at the discretion of the investigator, is deemed to be of childbearing potential or , the male subject who is nonsterilized and sexually active with a female partner of childbearing potential

CONFIDENTIAL

- Clinical chemistry
- Pelvic/Testicular ultrasonography
- Estradiol or testosterone.
- Injection of investigational drug by investigator or investigator's designee
- AE assessment

9.3.5 Treatment Phase - Visit 5 (Week 36)

Visit 5 will take place on Week 36. The following procedures will be performed and documented during this visit:

- Vital signs.
- Weight, height.
- Concomitant medications.
- Tanner staging evaluation
- Pregnancy avoidance counseling, for female subject who, at the discretion of the investigator, is deemed to be of childbearing potential or , the male subject who is nonsterilized and sexually active with a female partner of childbearing potential.
- ECG.
- LH and FSH.
- Estradiol or testosterone.
- Injection of investigational drug by investigator or investigator's designee
- AE assessment.

9.3.6 Treatment Phase - Visit 6 (Week 48)

Visit 6 will take place on Week 48. The following procedures will be performed and documented during this visit:

- Physical examination.
- Vital signs.
- Weight, height.
- Concomitant medications.
- Predicted adult height.
- Tanner staging evaluation.

- Bone age.
- Hematology.
- Urine analysis
- Pregnancy avoidance counseling, for female subject who, at the discretion of the investigator, is deemed to be of childbearing potential or , the male subject who is nonsterilized and sexually active with a female partner of childbearing potential
- Clinical chemistry
- Pelvic/testicular ultrasonography.
- Estradiol or testosterone.
- Injection of investigational drug by investigator or investigator's designee
- AE assessment

9.3.7 Treatment Phase - Visit 7 (Week 60)

Visit 7 will take place on Week 60. The following procedures will be performed and documented during this visit:

- Vital signs.
- Weight, height.
- Concomitant medications.
- Tanner staging evaluation.
- Pregnancy avoidance counseling, for female subject who, at the discretion of the investigator, is deemed to be of childbearing potential or , the male subject who is nonsterilized and sexually active with a female partner of childbearing potential
- ECG.
- LH and FSH
- Estradiol or testosterone.
- Injection of investigational drug by investigator or investigator's designee.
- AE assessment.

9.3.8 Treatment Phase - Visit 8 (Week 72)

Visit 8 will take place on Week 72. The following procedures will be performed and documented during this visit:

- Vital signs.

CONFIDENTIAL

- Weight, height.
- Concomitant medications.
- Tanner staging evaluation.
- Bone age.
- Hematology.
- Pregnancy avoidance counseling, for female subject who, at the discretion of the investigator, is deemed to be of childbearing potential or , the male subject who is nonsterilized and sexually active with a female partner of childbearing potential.
- Clinical chemistry.
- Pelvic/testicular ultrasonography.
- Estradiol or testosterone.
- Injection of investigational drug by investigator or investigator's designee.
- AE assessment.

9.3.9 Treatment Phase - Visit 9 (Week 84)

Visit 9 will take place on Week 84. The following procedures will be performed and documented during this visit:

- Vital signs.
- Weight, height.
- Concomitant medications.
- Tanner staging evaluation.
- Pregnancy avoidance counseling, for female subject who, at the discretion of the investigator, is deemed to be of childbearing potential or , the male subject who is nonsterilized and sexually active with a female partner of childbearing potential.
- LH and FSH.
- Estradiol or testosterone.
- Injection of investigational drug by investigator or investigator's designee.
- AE assessment.

9.3.10 Treatment Phase - Visit 10 (Week 96, last dose)

Visit 10 will take place on Week 96. The following procedures will be performed and documented during this visit:

CONFIDENTIAL

- Vital signs.
- Weight, height.
- Concomitant medications.
- Predicted adult height.
- Tanner staging evaluation.
- Bone age.
- Pregnancy avoidance counseling, for female subject who, at the discretion of the investigator, is deemed to be of childbearing potential or , the male subject who is nonsterilized and sexually active with a female partner of childbearing potential.
- ECG.
- Pelvic/testicular ultrasonography.
- Estradiol or testosterone.
- Stimulation test.
- Injection of investigational drug by investigator or investigator's designee.
- AE assessment.

9.3.11 Final Safety Visit or Early Termination - Visit 11 (Week 100)

Visit 11 will take place on Week 100. The following procedures will be performed and documented during this visit:

- Physical examination.
- Vital signs.
- Weight, height.
- Concomitant medications.
- Tanner staging evaluation.
- Hematology.
- Urine analysis.
- Pregnancy avoidance counseling, for female subject who, at the discretion of the investigator, is deemed to be of childbearing potential or , the male subject who is nonsterilized and sexually active with a female partner of childbearing potential.
- Clinical chemistry.
- Pelvic/testicular ultrasonography.

CONFIDENTIAL

- Estradiol or testosterone.
- Bone mineral density.
- Serum bone metabolism biomarker.
- AE assessment.

The Final Visit will be performed on Week 100 or at the Early Termination Visit. The following procedures will be performed and documented:

For all subjects receiving study medication, the investigator must complete the End of Study eCRF page.

9.3.12 Observational Follow-up

Observational Follow-up will begin the first day after the Final safety Visit.

During the observation follow-up the patient visits to the referring physician are not pre-specified by the study protocol, but will follow usual clinical practice. It is anticipated that the CPP patients will visit the site for check up at least every 24 weeks. All patient-care decisions, including diagnostic and therapeutic interventions, will be made by and conducted at the discretion of the participating study physicians according to their clinical judgement and the local standard of medical care.

Data should be entered into the database, at the patients' visits (at least every 24 weeks) and at the end of data collection. However, no patients will be excluded based on different reporting frequencies. The source of the data is the patient medical record.

The following data will be recorded if it is collected as part of routine clinical practice:

- Physical examination.
- Vital signs.
- Weight, height.
- Predicted adult height.
- Tanner staging evaluation.
- Bone age.
- Hematology.
- Clinical chemistry.
- ECG.
- Pelvic/testicular ultrasonography.
- Estradiol or testosterone.

- AE assessment.

After the last dose of leuprorelin treatment, subjects will be followed up annually and conduct the following procedure until stable puberty is reached.

The following data will be recorded when it is collected as part of routine clinical practice:

- Tanner staging.
- Height and weight.
- Menstrual history for girls.
- Pelvic ultrasongraphy for girls.

The observational follow-up is not included in this study. The requirement has not been determined as yet. If long term observational follow-up is performed then the patients will undergo a further Consent process, including new Parent/Patient Information sheet.

10.0 PRETREATMENT EVENTS AND ADVERSE EVENTS

10.1 Definitions

10.1.1 PTEs

A PTE is defined as any untoward medical occurrence in a clinical investigation subject who has signed informed consent to participate in a study but prior to administration of any study medication; it does not necessarily have to have a causal relationship with study participation.

10.1.2 AEs

An AE is defined as any untoward medical occurrence in a clinical investigation subject administered a drug; it does not necessarily have to have a causal relationship with this treatment.

An AE can therefore be any unfavorable and unintended sign (eg, a clinically significant abnormal laboratory finding), symptom, or disease temporally associated with the use of a drug whether or not it is considered related to the drug.

10.1.3 Additional Points to Consider for PTEs and AEs

An untoward finding generally may:

- Indicate a new diagnosis or unexpected worsening of a pre-existing condition. (Intermittent events for pre existing conditions underlying disease should not be considered PTEs or AEs.)
- Necessitate therapeutic intervention.
- Require an invasive diagnostic procedure.
- Require discontinuation or a change in dose of study medication or a concomitant medication.
- Be considered unfavorable by the investigator for any reason.
- PTEs/AEs caused by a study procedure (eg, a bruise after blood draw) should be recorded as a PTE/AE.

Diagnoses vs signs and symptoms:

- Each event should be recorded to represent a single diagnosis. Accompanying signs (including abnormal laboratory values or ECG findings) or symptoms should NOT be recorded as additional AEs. If a diagnosis is unknown, sign(s) or symptom(s) should be recorded appropriately as a PTE(s) or as an AE(s).

Laboratory values and ECG findings:

- Changes in laboratory values or ECG parameters are only considered to be PTEs or AEs if they are judged to be clinically significant (ie, if some action or intervention is required or if the investigator judges the change to be beyond the range of normal physiologic fluctuation). A laboratory re-test and/or continued monitoring of an abnormal value are not considered an

CONFIDENTIAL

intervention. In addition, repeated or additional noninvasive testing for verification, evaluation or monitoring of an abnormality is not considered an intervention.

- If abnormal laboratory values or ECG findings are the result of pathology for which there is an overall diagnosis (eg, increased creatinine in renal failure), the diagnosis only should be reported appropriately as a PTE or as an AE.

Preeexisting conditions:

- Pre-existing conditions (present at the time of signing of informed consent) are considered concurrent medical conditions and should NOT be recorded as PTEs or AEs. Baseline evaluations (eg, laboratory tests, ECG etc.) should NOT be recorded as PTEs unless related to study procedures. However, if the subject experiences a worsening or complication of such a concurrent condition, the worsening or complication should be recorded appropriately as a PTE (worsening or complication occurs before start of study medication) or an AE (worsening or complication occurs after start of study medication). Investigators should ensure that the event term recorded captures the change in the condition (eg, “worsening of...”).
- If a subject has a pre-existing episodic condition (eg, asthma, epilepsy) any occurrence of an episode should only be captured as a PTE/AE if the episodes become more frequent, serious or severe in nature, that is, investigators should ensure that the AE term recorded captures the change in the condition from Baseline (eg “worsening of...”).
- If a subject has a degenerative concurrent condition (eg, cataracts, rheumatoid arthritis), worsening of the condition should only be captured as a PTE/AE if occurring to a greater extent to that which would be expected. Again, investigators should ensure that the AE term recorded captures the change in the condition (eg, “worsening of...”).

Worsening of PTEs or AEs:

- If the subject experiences a worsening or complication of a PTE after starting administration of the study medication, the worsening or complication should be recorded appropriately as an AE. Investigators should ensure that the AE term recorded captures the change in the condition (eg, “worsening of...”).
- If the subject experiences a worsening or complication of an AE after any change in study medication, the worsening or complication should be recorded as a new AE. Investigators should ensure that the AE term recorded captures the change in the condition (eg, “worsening of...”).

Changes in severity of AEs /Serious PTEs:

- If the subject experiences changes in severity of an AE/serious PTE, the event should be captured once with the maximum severity recorded.

Preplanned surgeries or procedures:

- Preplanned procedures (surgeries or therapies) that were scheduled prior to signing of informed consent are not considered PTEs or AEs. However, if a preplanned procedure is performed early (eg, as an emergency) due to a worsening of the pre-existing condition, the worsening of the condition should be captured appropriately as a PTE or an AE. Complications resulting from any planned surgery should be reported as AEs.

Elective surgeries or procedures:

- Elective procedures performed where there is no change in the subject's medical condition should not be recorded as PTEs or AEs, but should be documented in the subject's source documents. Complications resulting from an elective surgery should be reported as AEs.

Insufficient clinical response (lack of efficacy):

- Insufficient clinical response, efficacy, or pharmacologic action, should NOT be recorded as an AE. The investigator must make the distinction between exacerbation of pre-existing illness and lack of therapeutic efficacy.

Overdose:

- Cases of overdose with any medication without manifested side effects are NOT considered PTEs or AEs, but instead will be documented on an Overdose page of the eCRF. Any manifested side effects will be considered PTEs or AEs and will be recorded on the AE page of the eCRF.

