9.1.7 Documentation of Concurrent Medical Conditions

Concurrent medical conditions are those significant ongoing conditions or diseases that are present at signing of informed consent. This includes clinically significant laboratory, electrocardiogram (ECG), or physical examination abnormalities noted at screening examination. The condition (ie, diagnosis) should be described and recorded in the eCRF.

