10.1.4 SAEs

An SAE is defined as any untoward medical occurrence that at any dose:

1. Results in DEATH.
2. Is LIFE THREATENING.
 - The term "life threatening" refers to an event in which the subject was at risk of death at the time of the event; it does not refer to an event that hypothetically might have caused death if it were more severe.
3. Requires inpatient HOSPITALIZATION or prolongation of existing hospitalization.
4. Results in persistent or significant DISABILITY/INCAPACITY.
5. Leads to a CONGENITAL ANOMALY/BIRTH DEFECT.
6. Is an IMPORTANT MEDICAL EVENT that satisfies any of the following:

CONFIDENTIAL

- May require intervention to prevent items 1 through 5 above.
- May expose the subject to danger, even though the event is not immediately life threatening or fatal or does not result in hospitalization.
- Includes any event or synonym described in the Takeda Medically Significant AE List (Table 10.a).

Table 10.a Takeda Medically Significant AE List

Term	
Acute respiratory failure/acute respiratory distress syndrome	Hepatic necrosis
Torsade de pointes / ventricular fibrillation / ventricular tachycardia	Acute liver failure Anaphylactic shock
Malignant hypertension	Acute renal failure
Convulsive seizure	Pulmonary hypertension
Agranulocytosis	Pulmonary fibrosis
Aplastic anemia	Confirmed or suspected endotoxin shock
Toxic epidermal necrolysis/Stevens-Johnson syndrome	Confirmed or suspected transmission of infectious agent by a medicinal product Neuroleptic malignant syndrome / malignant hyperthermia Spontaneous abortion / stillbirth and fetal death

PTEs/AEs that fulfill 1 or more of the serious criteria above are also to be considered SAEs and should be reported and followed up in the same manner (see Sections 10.2.2 and 10.3).

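### Sections 10.1.3 and 10.1.4 conflict on a serious episode that matches a child's earlier pattern of epilepsy or asthma, so a listed SAE such as a convulsive seizure can go unreported

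*Protocol*

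**What the plan says.** **Protocol 10.1.3, episodic conditions.** The rule for a pre-existing episodic condition reads, in part, "eg, asthma, epilepsy) any occurrence of an episode should only be captured as a PTE/AE if the episodes become more frequent, serious or severe". The sentence goes on to require that the recorded term show the change from Baseline.

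**Protocol 10.1.3, opening list.** A parenthesis under the first bullet is broader: "Intermittent events for pre existing conditions underlying disease should not be considered PTEs or AEs".

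**Protocol 10.1.3, pre-existing conditions in general.** Deterioration is recorded: "if the subject experiences a worsening or complication of such a concurrent condition, the worsening or complication should be recorded appropriately as a PTE", or as an AE once study medication has started.

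**Protocol 10.1.4.** The definition opens "An SAE is defined as any untoward medical occurrence that at any dose" and lists its criteria. Criterion 3 is "Requires inpatient HOSPITALIZATION or prolongation of existing hospitalization". Criterion 6 "Includes any event or synonym described in the Takeda Medically Significant AE List (Table 10.a"), and that table contains convulsive seizure. Neither criterion refers to the subject's history. SAP 6.5.1 and its Table 6.b repeat the definition and the seizure term, also without an exception.

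**Protocol 9.1.7.** For concurrent conditions, "The condition (ie, diagnosis) should be described and recorded in the eCRF". It does not ask for the number or severity of earlier episodes.

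**The concern.** Epilepsy is the protocol's own example of a condition whose unchanged episodes are not captured. Its typical event is also on the protocol's own list of events that are always medically significant. Two sites could each follow a paragraph correctly and classify the same seizure differently.

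Safety is the primary objective, the study is open label with no comparator, and Section 11.0 states that no data monitoring committee is used. The SAP tabulates what was entered as an AE, so the analysis cannot recover an SAE that never reached the AE page. Such an event would also miss the 24-hour reporting in 10.2.2.

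**Working it through.** The plan has no figure to reproduce. It gives no expected SAE rate and no number of children with epilepsy or asthma. The check is a comparison of the two sections, followed by a range for size.

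**Step 1. The same events under each section (after first dose).**

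| Event | 10.1.3 | 10.1.4 | Agree? |
|---|---|---|---|
| First convulsive seizure, no history | captured (new diagnosis) | SAE | yes |
| Known epilepsy, convulsive seizures now more frequent | captured | SAE | yes |
| Known convulsive epilepsy, seizure at earlier pattern | not captured | SAE (Table 10.a) | **no** |
| Known asthma, first admission | captured (more serious) | SAE | yes |
| Known asthma, admission matching earlier admissions | not captured | SAE (criterion 3) | **no** |
| Known asthma, mild episode at earlier pattern | not captured | not an SAE | yes |

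The conflict is confined to serious episodes that match the child's earlier pattern.

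**Step 2. Is there a tie-breaker?**
- The closing sentence of 10.1.4 applies the serious criteria to PTEs and AEs. On that reading, an episode already ruled out as an AE never reaches the seriousness test.
- Section 10.2.2 requires a report whenever an SAE occurs in the collection period, which points the other way.
- SAP 6.5.1 restates the definition and gives no precedence.

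Nothing settles it.

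**Step 3. Could such children be enrolled?** Section 7.2 names neither epilepsy nor asthma. Exclusions 4 and 5 let the investigator exclude on medical history or on a concomitant condition of unacceptable risk. Some would be removed, but not by rule.

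**Step 4. Size for SAEs.** N = 300 (Protocol 13.3). Let u be the number of children whose serious episode goes unrecorded (assumed). If they have no other recorded SAE, the SAE percentage falls by u/300: 0.33 points for u = 1 and 1.0 point for u = 3. Exact (Clopper-Pearson) 95% limits, used only for scale:

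| Children with an SAE | % | 95% limits |
|---|---|---|
| 0 | 0 | 0 to 1.22 |
| 1 | 0.33 | 0.01 to 1.84 |
| 2 | 0.67 | 0.08 to 2.39 |
| 3 | 1.0 | 0.21 to 2.89 |

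If three children truly have an SAE and one is missed, a third of the count is lost. An event with a true rate of 1% is seen at least once with probability 1 − 0.99^300 = 0.951, so the study sits where single events carry the information.

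**Step 5. Size for the primary endpoint.** A child counts once for any TEAE. A missed episode matters only if that child has no other recorded TEAE. With p the assumed share who do have another, the shift is u(1 − p)/300:
- u = 1: 0.7/300 = 0.23 points at p = 30%; 0.1/300 = 0.03 points at p = 90%.
- u = 3: 2.1/300 = 0.70 points at p = 30%; 0.3/300 = 0.10 points at p = 90%.

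The 95% half-width on a percentage from 300 children is 5.3 points at 30%, 5.8 at 50% and 3.6 at 90%.

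**The case against.** The best defence is that the sections are nested: 10.1.3 decides what is an AE and 10.1.4 then grades it. Leaving unchanged background episodes off the AE page would then be a deliberate convention. The broad parenthesis can be read as a general statement that the later bullet makes specific. The opening list of 10.1.3 also gives a site grounds to record anything that needs treatment or that the investigator considers unfavourable. One could add that the episodic rule itself mentions seriousness, so a serious episode is captured anyway.

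Part of this stands. The nested reading is possible, and the parenthesis is not an independent third rule. But the nested reading is nowhere stated, and 10.1.4 defines an SAE from any untoward occurrence, not from a recorded AE. The word serious does not rescue the rule, because the test is whether episodes have become so and the term must show change from Baseline.

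A reader might infer that any asthma admission or seizure in a child with that history is lost. The documents do not support this: a first or worse episode is captured under the episodic rule, and a worsening or complication under the preceding bullet.

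It is also too strong to say that a missed event would leave no trace. Concomitant medication and concurrent conditions are recorded and listed, so treatment of an episode may show there, though not as an AE.

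**Conclusion.** The contradiction is real and narrow. For a serious episode at the child's earlier pattern, with a convulsive seizure in known convulsive epilepsy as the clearest case, the two sections give opposite instructions and nothing ranks them. SAE reporting, SAE tables and listings, preferred-term counts and event rates per 100 patient years can be incomplete.

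A reader might conclude that SAEs and the primary TEAE percentage are under-counted. The documents support only that SAEs can be. They do not say how many such children enrol, exclusions 4 and 5 may remove some, and a site that follows 10.1.4 literally would report the event. Population prevalence would not fill the gap, since it counts diagnoses and not missed serious episodes. The effect on the primary percentage is likely negligible: 0.03 to 0.23 points per missed child if 30% to 90% of such children have another TEAE, against a half-width of 3.6 to 5.8 points. Both u and p are assumptions. No sample-size figure is affected.

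**What to change.** Reconcile 10.1.3 with 10.1.4 by adding to the episodic-condition bullet:

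> An untoward episode that meets a seriousness criterion in 10.1.4 or is a Table 10.a term is recorded as a PTE or AE and reported under 10.2.2 even if it matches the subject's prior pattern; preplanned and elective procedures remain as in this section.

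Make the parenthesis in the opening list of 10.1.3 subject to this bullet. The limit to untoward episodes, and the last clause, avoid a clash with the rules on planned and elective procedures. Naming PTEs covers the time between consent and first dose, because 10.2.2 sends serious PTEs through the SAE procedure. SAP 6.5.1 can stay as it is.

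Optionally, an eCRF field for prior episode frequency and severity would give the comparison a documented baseline; the fix does not depend on it.

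The cost is one sentence, one cross-reference and a few extra SAE reports of episodes that may be background disease. It changes recording only, not treatment.
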